3.2. Secondary Endpoints

3.2.1. Secondary Efficacy Endpoints (Part A: Blinded Phase Only)

The secondary efficacy endpoints in Part A have been analyzed and demonstrated consistent vaccine efficacy of mRNA-1273, please refer to SAP Version 2.0 and Blinded phase (Part A) CSR. The secondary efficacy objectives/endpoints in Part A included:

- The VE of mRNA-1273 to prevent severe COVID-19, defined as first occurrence of COVID-19 starting 14 days after the second dose of IP, (as per the primary endpoint) AND any of the following:
 - Clinical signs indicative of severe systemic illness, Respiratory Rates ≥ 30 per minute, Heart Rate ≥ 125 beats per minute, SpO₂ $\leq 93\%$ on room air at sea level or PaO₂/FIO₂ < 300 mm Hg, OR
 - Respiratory failure or Acute Respiratory Distress Syndrome (ARDS), (defined as needing high-flow oxygen, non-invasive or mechanical ventilation, or ECMO), evidence of shock (systolic blood pressure < 90 mmHg, diastolic BP < 60 mmHg or requiring vasopressors), OR
 - Significant acute renal, hepatic or neurologic dysfunction, OR
 - Admission to an intensive care unit or death.
- The VE of mRNA-1273 to prevent the first occurrence of either COVID-19 or SARS-CoV-2 infection starting 14 days after the second injection of IP. This endpoint is a combination of COVID-19, defined as for the primary endpoint, and asymptomatic SARS-CoV-2 infection, determined by seroconversion assessed by bAb levels against SARS-CoV-2 as measured by a ligand-binding assay specific to the SARS-CoV-2 nucleocapsid protein and with a negative NP swab sample for SARS-CoV-2 at Day 1 .
- The VE of mRNA-1273 to prevent the secondary case definition of COVID-19 starting 14 days after the second injection of IP. The secondary case definition of

COVID-19 is defined as at least one of the following systemic symptoms: fever (temperature $\geq 38^{\circ}\text{C}$), or chills, cough, shortness of breath or difficulty breathing, fatigue, muscle aches or body aches, headache, new loss of taste or smell, sore throat, nasal congestion or rhinorrhea, nausea or vomiting, or diarrhea AND a positive NP swab, nasal swab, or saliva sample (or respiratory sample, if hospitalized) for SARS-CoV-2 by RT-PCR.

- The VE of mRNA-1273 to prevent death due to a cause directly attributed to a complication of COVID-19, starting 14 days after the second IP dose.
- The VE of mRNA-1273 to prevent the first occurrence of COVID-19 starting 14 days after the first dose of IP.
- The VE of mRNA-1273 to prevent the first occurrence of COVID-19 starting 14 days after the second dose of IP regardless of evidence of prior SARS-CoV-2 infection determined by serologic titer against SARS-CoV-2 nucleocapsid or RT-PCR at baseline.
- The VE to prevent the first occurrence of SARS-CoV-2 infection in the absence of symptoms defining COVID-19 starting 14 days after the second IP dose. SARS-CoV-2 infection will be determined by seroconversion assessed by bAb levels against SARS-CoV-2 as measured by a ligand-binding assay specific to the SARS-CoV-2 nucleocapsid protein and with a negative NP swab sample for SARS-CoV-2 at Day 1.

3.2.2. Secondary Immunogenicity Endpoints

The secondary immunogenicity objective (Part A), to evaluate the immunogenicity of 2 doses of mRNA-1273 given 28 days apart, have been evaluated and summarized in the Part A CSR (dated 03 Aug 2021). Immune response to mRNA-1273 have been evaluated using binding and neutralizing antibodies specific to the SARS-CoV-2 proteins at baseline (pre-vaccination), 1 month after Dose 1 (Day 29) and 1 month after Dose 2 (Day 57) in a pre-select stratified random subcohort of participants including the following antigens:

- Serum bAb levels against SARS-CoV-2 as measured by ligand-binding assay specific to the SARS-CoV-2 S protein (MSD).
- Serum nAb titer against SARS-CoV-2 as measured by pseudovirus neutralization assays (PsVNA).

Blood samples for immunogenicity assessments continue as planned at the time points indicated in the SoEs of the protocol.

The immunogenicity endpoints (Part A) includes:

- Geometric mean titer (GMT) of SARS-CoV-2-specific binding and neutralizing antibodies (bAb and nAb)
- Geometric mean fold rise (GMFR) of SARS-CoV-2-specific bAb and nAb relative to Day 1.
- Seroresponse rate as compared to baseline (pre-vaccination/pre-Dose 1)

The following secondary immunogenicity endpoints at the specified timepoint are specifically for Part C immunogenicity analyses:

- GMT of post-booster antibodies at BD-Day 29 as compared to post-primary series mRNA-1273 at Day 57
- Seroresponse rate of booster from pre-Dose 1 of mRNA-1273 primary series at post-booster BD-Day 29 from Pre-vaccination/Pre-Dose 1 of the primary series as compared to post-Dose 2 (at Day 57) from Pre-vaccination/Pre-Dose 1 of the primary series in recipients of mRNA-1273.
 - Seroresponse is defined as at least 4-fold rise from pre-Dose 1 of mRNA-1273 primary series, for those below the LLOQ to $\geq 4 \times$ LLOQ
 - Additional definitions of Seroresponse of a booster may be used and the details are provided in Section 5.5.2.1.1

Given the emergence of new SARS-CoV-2 variants in multiple waves, immune response of mRNA-1273 as measured by nAb and/or bAb against select variant strains (of interest)

would be of interest. If these data (nAb and/or bAb against variant strains) are available, respective endpoints similar to those listed above against prototype strains will be assessed.

3.3. Endpoints to assess effectiveness of mRNA-1273

Effectiveness of the primary series and a booster (Part C) will be evaluated by the following endpoints with details specified in section 5.3:

- COVID-19
- severe COVID-19
- COVID-19 or SARS-CoV-2 infection, serologically confirmed SARS-CoV-2 infection or COVID-19 regardless of symptomatology or severity
- COVID-19 based on a secondary (less restrictive) definition of COVID-19
- death caused by COVID-19
- Asymptomatic SARS-CoV-2 infection

3.4. Exploratory Endpoints

The following exploratory objective/endpoints for Part A have been evaluated and results have been presented in the final blinded phase CSR (dated 03 Aug 2021) or have been included in accepted/published articles:

- VE of mRNA-1273 to reduce duration and presence/severity of COVID-19 symptoms
- VE of mRNA-1273 against Burden of Disease
- VE of mRNA-1273 against Burden of Infection
- VE of mRNA-1273 against all-cause mortality
- Effect of mRNA-1273 against viral load (Pajon, 2021)
- Preliminary analysis of immune response markers as correlates of risk has been performed and the results are published (Gilbert, 2021)

3.5. Overall Study Design

This is a 3-part Phase 3 study: Part A, Part B and Part C. Participants in Part A, the Blinded Phase of this study are blinded to their treatment assignment. Given that the primary efficacy endpoint for mRNA-1273 against COVID-19 was met per the protocol-defined interim analysis, Part B, the Open-Label (OL) Observational Phase of this study is designed to offer participants who received placebo in Part A of this study and who meet EUA eligibility, an option to request open-label mRNA-1273 (Figure 1). Part C, the booster dose (BD) Phase, is designed to offer eligible participants the option to receive a booster dose of mRNA-1273.

Study design of Part A is described in protocol section 4.1.1 and SAP Version 2.0 section 4.1.1 .

3.5.1. Part B, the Open-Label Observational Phase

All participants will proceed to Part B, the Open-Label Observational Phase of the study, starting with a Participant Decision clinic visit (PDV) (Figure 2). Participants are given the option to be unblinded to their original treatment. A NP swab for RT-PCR for SARS-CoV-2 and a blood sample for serology are collected prior to unblinding.

Participants who are unblinded, only received placebo in the blinded phase, are EUA eligible, and request to receive mRNA-1273 will proceed to receive two doses of mRNA-1273 in Part B (Table 21 supplemental scheduled of event in the protocol).

Participants who are unblinded and received only one dose of mRNA-1273 in the blinded phase, are EUA eligible, and request to receive mRNA-1273 will proceed to receive one dose of mRNA-1273 in Part B (Table 22 modified supplemental scheduled of event in the protocol).

All participants remain on their original schedule of event to complete 24 months of follow-up after the second injection of IP; study participants who enter the Supplemental or Modified Supplemental schedule of event as described above do so in addition to their

original schedule of event. Accordingly, all study participants will complete the full study follow-up to 24 months after the second dose of their original inoculation (mRNA-1273 or placebo).

Solicited adverse reactions (ARs) after each injection of mRNA-1273 are not collected in the open-label phase. Participants will use an electronic diary (eDiary) to prompt an unscheduled clinic visit if experiencing any symptoms of COVID-19. Surveillance for COVID-19 will be performed through weekly contacts with the participants via a combination of telephone calls and completion of an eDiary starting at Day 1 through the end of the study. An illness visit will be scheduled if the participant is experiencing COVID-19 symptoms.

[figure not shown]
3.5.2. Part C, the Booster Dose Phase

All participants will be asked to schedule BD-1 (BD Day 1) visit as the start of Part C, the Booster Dose Phase. Eligible participants will be provided an option to receive BD consisting of a single 50 µg dose of mRNA-1273.

After the BD 1 visit, participants who do not receive a BD will continue with the Part C schedule of events with the exception of the BD-1a (BD Day 4) visit and blood draw and the safety calls (Table 23 in the protocol).

[figure not shown]
At the BD 1 visit, participants who request a BD, are eligible and have no contraindications to further dosing (Section 7.1 in the protocol) will have subsequent study site visits and complete scheduled activities (subject to investigational vaccine availability) according to the Part C schedule of events (Table 23 in the protocol).

Figure 1 Study Flow Diagram: Part A, the Blinded Phase followed by Part B, the Open-Label Phase Including Part C, the Booster Dose Phase

Abbreviations: BD = booster dose visit; EUA = emergency use authorization

Figure 2 Part B, the Open-Label Observational Phase, and Part C, the Booster Dose Phase

- ^a All participants are encouraged to remain in the study.
- ^b All participants are given the option to be unblinded to treatment received in Part A: Blinded Phase.
- ^c All participants are counselled about the importance of continuing other public health measures to limit the spread of disease including physical-social distancing, wearing a mask, and hand-washing.
- ^d All participants sign a revised informed consent form.
- ^e All participants consent to provide a nasopharyngeal swab and a blood sample for immunologic analysis.
- ^f mRNA-1273 recipients who only received 1 dose of the mRNA-1273 vaccine will receive the second dose of mRNA-1273 vaccine.
- ^g Placebo recipients who request to receive mRNA-1273 and meet eligibility will comply with a Supplemental Schedule of Events in addition to the Original Study Schedule of Events included in the Clinical Study Protocol.
- ^h Original Study Schedule of Events are included in the Clinical Study Protocol

i Procedures required or not required based on receipt of the booster dose are clarified in the Part C Supplemental Schedule of Events included in the Clinical Study Protocol

3.6. Statistical Hypothesis (Part A)

For the primary efficacy objective of the blinded phase (Part A), the null hypothesis of this study is the VE of mRNA-1273 to prevent first occurrence of COVID-19 is $\leq 30\%$, i.e.

$H_0^{\text{efficacy}}: \text{VE} \leq 0.3$.

The primary efficacy objective has been demonstrated based on pre-specified success criterion at the interim analysis based on 95 adjudicated cases (data snapshot 11 Nov 2020).

The primary analysis (data snapshot 25 Nov 2020) and the final analysis of the blinded phase (DBL 04 May 2021) have consistent results on vaccine efficacy, confirming persistent, high efficacy over the blinded phase.

3.7. Sample Size and Power

Please refer to the protocol and SAP Version 2.0 for details.

3.8. Randomization

Please refer to the protocol and SAP Version 2.0 for details.

3.9. Blinding and Unblinding

Part A of this study is an observer-blind part. The investigator, study staff, study participants, site monitors, and Sponsor personnel (or its designees) were blinded to the IP administered until unblinding in Part B, with the certain exceptions specified in Section 6.2.8 of the protocol. Refer to SAP Version 2.0 for more details.

Part B and Part C of the study is open-label.

4. Analysis Populations

The following analysis sets have been defined in SAP Version 2.0. Refer to SAP Version 2.0 for details.

- Randomization Set
- Full Analysis Set (FAS)
- Modified Intent-to-Treat (mITT) Set
- Per-protocol (PP) Set
- Per-Protocol Random Subcohort for Immunogenicity (PPRSI)
- Safety Set
- Solicited Safety Set

The following analysis sets are defined in this SAP for Part C:

- Part C Safety Set
- Part C Per-Protocol Random Subcohort for Immunogenicity (Part C PPRS)
- Part C Per-Protocol Immunogenicity Subset (Part C PPIS)
- Part C Per-Protocol Immunogenicity Subset – Pre-booster SARS-CoV-2 negative (Part C PPIS-Neg)
- Part C Per-Protocol Set (Part C PPS)

The following analysis sets are defined in this SAP for Primary Series (for those randomized to mRNA-1273 in Part A and those crossover to mRNA-1273 in Part B):

- Per Protocol Primary Series Set (PP Primary Series)
- Primary Series Safety Set

4.1. Part C Safety Set

The Part C Safety Set consists of participants who were randomized in Part A and received mRNA-1273 50 ug booster in Part C. The Part C Safety Set will be used for all analysis of safety in Part C.

4.2. Part C Per-Protocol Random Subcohort for Immunogenicity (Part C PPRSI)

The Part C PPRSI consists of participants who were in PPRSI in Part A defined in SAP Version 2.0, received booster in Part C, and did not have major PDs after Part A that impact major or critical data. Participants who did not receive 2 doses of the primary series of mRNA-1273, or did not receive Dose 2 of mRNA-1273 within [21, 42] days after Dose 1 would be excluded from Part C PPRSI.

Part C PPRSI may be used to summarize immune response after booster in Part C.

4.3. Part C Per-Protocol Immunogenicity Subset (Part C PPIS)

The Part C PPIS consists of participants who were in PPRSI in Part A (defined in SAP Version 2.0), randomized to mRNA-1273 in Part A, were baseline/pre-Day 1 SARS-CoV-2 negative and received booster in Part C.

Part C PPIS is a subset of PPRSI in Part A, and a subset of Part C PPRSI. Part C PPIS will be used to summarize immune response after booster in Part C

4.4. Part C Per-Protocol Immunogenicity Subset – Pre-booster SARS-CoV-2 Negative (Part C PPIS-Neg)

The Part C PPIS-Neg consists of participants who are in Part C PPIS and are pre-booster SARS-CoV-2 negative, defined as no virologic or serologic evidence of SARS-CoV-2 infection on or before BD-Day 1 (pre-booster), i.e. RT-PCR result is not positive if available at BD-Day 1 and a negative bAb specific to SARS-CoV-2 nucleocapsid (as measured by Roche Elecsys Anti-SARS-CoV-2 assay) on or before BD-Day 1.

Part C PPIS-Neg will be used for analysis of immune response to booster, especially, to be compared with immune response after primary series of mRNA-1273 to infer efficacy of a booster.

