8.2.6. Blood Sampling

The maximum planned volumes of blood sampled for immunogenicity analyses per participant are approximately 50 mL for 1 day, 100 mL for 28 days ([Table 16](#)), and 300 to 420 mL (dependent on participation in Part B and Part C) for the total study volume ([Table 4](#)).

Table 4: Maximum Planned Immunogenicity Blood Sampling Volumes per Participant by Visit

Study Visit Day	Table 16 D1	Table 16 D29	Table 16 D57	Table 17 D209	Table 17 D394	Table 18 D759	Total
Immunogenicity blood samples ^a	50 mL	50 mL	50 mL	50 mL	50 mL	50 mL	300 mL
Study Visit Day	Part B Day 1^b	Part B Day 29^b	Part B Day 57^b	NA	NA	NA	NA
Immunogenicity blood samples ^a	20 mL	20 mL	20 mL	NA	NA	NA	60 mL ^c
Study Visit Day	Part C Day 1^d	Part C Day 4^d	Part C Day 29^d	Part C Day 181^d	NA	NA	NA
Immunogenicity blood samples ^a	24 mL	8 mL	24 mL	24 mL	NA	NA	80 mL

Abbreviations: COVID-19 = coronavirus disease 2019; D = Day; NA = not applicable; RT-PCR = reverse transcriptase polymerase chain reaction; OL = open-label; SoE = schedule of events.

^a Additional blood samples (16 mL) will be taken at Illness Day 1 and Convalescent Visit Day 28 for those participants who report symptoms of COVID-19 and who have RT-PCR confirmed symptomatic COVID-19, respectively.

^b If a visit from SoE [Table 16](#) and [Table 17](#) and a Part B visit overlap, only the Part B sample will be taken (using the Part B kit). The exception would be if an Illness Day 1 or Convalescent Visit Day 28 overlapped with a Part B visit. In this case the Illness and Convalescent Visit Day 28 samples would be taken and the corresponding kits used.

- ^c For participants who received placebo during the Part A Blinded Phase and receive mRNA-1273 during Part B. Note that immunogenicity blood samples are collected only on OL-D1 and OL-D57 (Table 21) or OL-D1 and OL-D29 (Table 22) in Part B.
- ^d If a visit from SoE Table 17 and Table 18 and a Part C visit overlap, only the Part C sample will be taken (using the Part C kit). Exceptions would be if an Illness Day 1 or Convalescent Visit Day 28 overlapped with a Part C visit, in this case the Illness and Convalescent Visit Day 28 samples would be taken and corresponding kits used, or in the case of a Part C Day 4 visit, both sets of samples would need to be taken using both kits.

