The pre-booster SARS-CoV-2 status is defined as missing for subjects with both tests missing, or no Elecsys results on or before BD-Day 1 and RT-PCR not positive at pre-booster (at BD-Day 1). Please note the NP Swab at BD-Day 1 is optional, which is a limitation to detect the infections occurred prior to Part C.

Subjects with positive pre-booster SARS-CoV-2 status will be excluded from the Part C PP Set and Part C PPIS-Neg.

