5.3.1.2.2. Effectiveness of the booster

For Part C, analysis of COVID-19 after booster, Part C PP Set will be used. For Part C, participants at risk at the start of Part C are defined as participants who did not have COVID-19 and had no SARS-CoV-2 infection prior to Part C , i.e. negative pre-booster SARS-CoV-2 status. Similarly, incidence rates after booster, as well as by calendar months (if feasible), and by time periods of the following time intervals will be provided:

- After Booster

- Booster to <14 days after booster
- ≥14 days after Booster

Person-time, incidence rate, and 95% CI for incidence rate based on the exact method adjusting for person-time will be provided by treatment cohort. Number and incidence rates of COVID-19 starting 14 days after Booster will also be provided by calendar months along with 2 additional time intervals associating with pre-omicron and omicron variant waves: 01-Sep-2021 to 30-Nov-2021 and 01-Dec-2021 to data cutoff date. The non-parametric Kaplan-Meier method will be used to estimate cumulative incidences of time to first occurrence of COVID-19 curve in each treatment cohort.

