5.3.2.1.4. Derivation of asymptomatic SARS-CoV-2 infection

Asymptomatic SARS-CoV-2 infection is identified by absence of symptoms and infections as detected by seroconversion or positive RT-PCR at scheduled visits applicable to individual treatment cohorts for Part B, Part C, and analysis of primary series with corresponding analysis periods:

- Absent of symptoms (no COVID-19 symptom for either efficacy endpoint of COVID-19, or secondary definition of COVID-19),
- AND at least one from below:

- Post-baseline positive RT-PCR at scheduled visits, or
- Seroconversion (bAb specific to SARS-CoV-2 nucleocapsid) at scheduled visits (PDV, OL Day 29, and OL Day 57 in Part B; BD Day 1, BD Day 29, and BD Day 181 in Part C), when blood samples for immunogenicity are collected.

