5.5. Immunogenicity Analysis

The secondary immunogenicity objective (Part A), to evaluate the immunogenicity of 2 doses of mRNA-1273 given 28 days apart, have been evaluated and summarized in the Part A CSR (dated 03 Aug 2021) using the Per-protocol stratified random subcohort (PPRSI). mRNA-1273 was highly immunogenic as measured by both bAb and nAb in both SARS-CoV-2 baseline-negative and baseline-positive individuals, as indicated by increased bAb and nAb levels 1 month after first injection (Day 29) and 1 month after second injection (Day 57).

This SAP includes analyses of immunogenicity data to evaluate the immunogenicity of mRNA-1273 primary series and booster.

In principle, summary (descriptive statistics) will be provided for available immunogenicity data by timepoints in relative of primary series and booster dose respectively. Comparison or analysis to assess difference between groups (Section 5.5.3) will only be performed using the same assay from the same (central) testing lab.

For immune response to a booster, Part C PPIS (Part C Per-Protocol Immunogenicity Subset), defined in Section 4.3, will be used for summaries of immune response, and data will be presented by pre-booster SARS-CoV-2 status. Part C PPIS-Neg, Part C PPIS – Pre-booster SARS-CoV-2 Negative defined in Section 4.4, will be used as the primary analysis population for comparison of immune response, either as paired-comparison when a subject serves as his/her own control; or between-group comparison compared to post-primary series in Part A using mRNA-1273 subjects in PPRSI with negative baseline SARS-CoV-2 as historical control.

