5.5.3.2. Immunobridging of response of a Booster as compared to Primary Series

Immunobridging analyses of a booster as compared to the primary series will be performed using the neutralizing antibody titers (as measured by PsVNA) 28 days following the booster dose (BD-D29) to the corresponding titers 28 days following the second dose of the primary series (Day 57 of the blinded phase for the mRNA-1273 cohort).

Immunobridging analyses may also be performed using binding antibody specific to S-protein by MSD.

The following endpoints will be used for this analysis:

- Geometric mean titer (GMT)
- Seroreponse Rate (SRR)

For GMT:

In the situation that subjects in PPIS-Neg Set have the same specific nAb (e.g. PsVNA) at baseline/pre-Dose 1, 28 days after Dose 2 of primary series, pre-booster, 28 days after booster and other timepoints, GMT ratios will be calculated by back transforming the mean of within-subject paired differences of antibody titers on the logarithmic scale between post-booster Day 29 (of the booster phase) and Day 57 of primary series (Day 57 of the blinded phase for the mRNA-1273 cohort). CIs for the GMT ratio will be based on t-distribution of the log-transformed values then back transformed to the original scale for presentation.

Another approach is to compare the post-booster antibody titers in Part C with the post-primary series titers in baseline-SARS-CoV-2 negative mRNA-1273 participants. An analysis of covariance (ANCOVA) model will be performed using the Part C PPIS-Neg Set with baseline-SARS-CoV-2 negative mRNA-1273 participants in PPSI (considering as historical control). In the model, antibody titers at 28 days post-booster (BD-Day 29) and post-Dose 2 of primary series will be a dependent variable, and a group variable (Booster and mRNA-1273 primary series) will be the fixed effect, adjusting for age groups (< 65, ≥ 65 years). The GMT will be estimated by the geometric least square mean (GLSM) from the model and its corresponding 95% CI will be provided for each group. The GMR (ratio of GMTs) for Booster with respect to mRNA-1273 primary series will be estimated by the ratio of GLSM from the model and the corresponding 95% CI will be provided. The 95% CI for

GMR will be used to assess the between group difference in immune response 28 days post-booster as compared to 28 days post-Dose 2 of the primary series.

For Seroresponse:

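### The primary booster immunobridging set screens for infection only up to BD-Day 1, so an infection before the BD-Day 29 draw is credited to the booster

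*SAP*

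**What the plan says.** Protocol Section 9.5.3.2 makes Part C immunogenicity a noninferiority comparison of BD-Day 29 with Day 57. The lower 95% limit of the GMR must be at least 0.67, and the lower limit of the seroresponse rate (SRR) difference must exceed -10%. SAP Part B/C Section 5.5.3.2 adds a superiority conclusion when the lower limit of the GMR exceeds 1.

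SAP Part B/C Section 5.5 says that the set called Part C PPIS-Neg "will be used as the primary analysis population for comparison of immune response". Section 4.4 defines it: "The Part C PPIS-Neg consists of participants who are in Part C PPIS and are pre-booster SARS-CoV-2 negative", meaning "no virologic or serologic evidence of SARS-CoV-2 infection on or before BD-Day 1 (pre-booster"). Where the same assay is available at the needed visits, "GMT ratios will be calculated by back transforming the mean of within-subject paired differences of antibody titers". Otherwise the set is compared with baseline-negative mRNA-1273 participants from the Part A random subcohort (PPRSI) as a historical control.

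The parent sets (SAP Part A Section 6.7.2; SAP Part B/C Sections 4.2 and 4.3) add criteria on baseline status, dosing and major protocol deviations. None concerns infection after the booster.

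Elsewhere the same SAP does handle such infections. Section 5.3.1.1 censors Part C participants at early infection found by RT-PCR or nucleocapsid antibody at scheduled visits. Section 5.3.2.1.4 uses nucleocapsid seroconversion at "BD Day 1, BD Day 29, and BD Day 181 in Part C".

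**The concern.** The objective is to infer the effectiveness of a 50 µg booster from the antibody that follows it. Infection raises the same spike-directed antibody. The SAP accepts this for infection before the booster: it restricts the comparison to pre-booster negatives, and Section 5.1.3 notes a weakness of that screen ("Please note the NP Swab at BD-Day 1 is optional, which is a limitation to detect the infections occurred prior to Part C"). It does not carry the principle forward to the interval between the booster and the sample.

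A participant infected in that interval, whose titer has risen by the draw, stays in the primary set, and the rise is attributed to the vaccine. The error runs one way, toward noninferiority or superiority. Protocol Section 6.4.3 also exempts immunoglobulins and blood products given to treat COVID-19 from its list of per-protocol exclusions, so a treated case is not removed by that route.

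**Working it through.** **The plan's own figures.** The margin is 1/1.5 = 0.667, stated as 0.67. The documents give no sample size, power or infection rate for Part C immunobridging, so there is nothing further to reproduce.

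**Length of the gap.** BD-Day 29 is 28 days after the booster, with a window of -3/+14 days (Protocol Table 23). The scheduled draw can therefore fall 28 + 14 = 42 days after the booster.

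**Overlap with Omicron.** SAP Part B/C Section 5.3.1.2.2 uses the intervals "01-Sep-2021 to 30-Nov-2021 and 01-Dec-2021 to data cutoff date" for the pre-Omicron and Omicron waves. Counting back from 01-Dec-2021, 28 days gives 3 November and 42 days gives 20 October 2021. Only boosters from about late October or early November have a draw that reaches the Omicron period. Earlier infections act in the same direction.

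**Effect on the GMR.** If a share p of the set is infected and the titer of each is multiplied by r, the mean log titer rises by p·ln(r) and the GMR is multiplied by r^p. The true GMR at which the expected estimate equals 0.67 falls to 0.67/r^p.

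**Chance of a false claim.** At a true GMR of 0.67, the chance is Φ(p·ln(r)/(s/√n) - 1.96), with s² = SD² + p(1-p)(ln r)². The nominal value is 2.5%. The same expression gives the chance of a false superiority claim at a true GMR of 1.

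All of p, r, SD (of the paired log difference) and n are assumptions. The table uses SD = 1.0 and n = 300.

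| p | r | r^p | 0.67/r^p | False-claim chance |
|---|---|---|---|---|
| 2% | 2 | 1.014 | 0.661 | 4.3% |
| 5% | 2 | 1.035 | 0.647 | 8.6% |
| 5% | 4 | 1.072 | 0.625 | 20.9% |
| 10% | 4 | 1.149 | 0.583 | 60.1% |

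For p = 5%, r = 2: s = √(1 + 0.0475 × 0.480) = 1.011; 0.0347/(1.011/√300) = 0.59; Φ(0.59 - 1.96) = 8.6%. Over n = 150 to 900 and SD = 0.8 to 1.2, this row runs from 5.4% to 24.7%.

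**Is the Day 57 side equally affected?** In the paired analysis it is not: negativity through BD-Day 1 largely clears infection from the Day 57 titer but not from the BD-Day 29 titer. In the historical-control analysis PPRSI has no on-study infection screen either. The design rate on vaccine, 0.30% per 6 months (Protocol Table 6), implies only 0.30% × 56/182.5 = 0.09% infected in 56 days.

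**Effect on SRR.** The gain is at most p(1 - SRR): 0.05 × 0.10 = 0.5 percentage points at p = 5% and SRR = 90%.

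**At the expected response.** Protocol Sections 2.2.2 and 4.3 report that a 50 µg booster in Study 201 gave 1.7-fold the primary-series peak of this study. With SD = 1.0 and n = 150 to 900, the lower limit at GMR 1.7 is exp(0.531 - 1.96/√n) = 1.45 to 1.59, clear of both 0.67 and 1. The estimate itself would move from 1.70 to 1.76 at p = 5%, r = 2, or to 1.95 at p = 10%, r = 4.

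**The case against.** The strongest objection is that the conclusion would be the same either way. At a 1.7-fold response noninferiority passes with or without contamination, and no document suggests a booster response near 0.67. That stands, and it limits the consequence. It does not cover the size of the reported GMR, or variant titers: Section 5.5.1 analyses these in the same way, and the documents state no expected ratio for them.

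An infection shortly before the draw may also not yet have raised the titer, so the effective p is below the share infected. That stands too.

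Four stronger readings are tempting, and the documents do not support them:

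- **That the booster phase as a whole ran in the Omicron wave.** Part C was introduced by the amendment of 10 September 2021, and the share boosted late enough to overlap is not stated.
- **That samples up to 105 days after the booster routinely count as BD-Day 29.** That Appendix B window applies to unscheduled samples, and those from confirmed COVID-19 cases are preferably mapped to illness visits. It matters mainly for undetected infections.
- **That Protocol Table 4, footnote d, places illness titers in the comparison.** When an illness or convalescent visit coincides with a Part C visit, "in this case the Illness and Convalescent Visit Day 28 samples would be taken and corresponding kits used". This is a rule about kits and blood volume. It does not say that the result is analysed as the BD-Day 29 titer.
- **That a failing lower limit can simply be multiplied by r^p.** The factor applies to the point estimate, and mixing infected with uninfected participants widens the interval. With p = 10%, r = 5 and SD = 1.0, a limit of 0.58 becomes 0.669 at n = 150 and 0.673 at n = 300, whereas plain multiplication gives 0.68.

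**Conclusion.** The gap is real, and no other section closes it. The primary immunobridging set has no rule for infection between BD-Day 1 and the BD-Day 29 draw, although the SAP applies one to effectiveness and the serology needed is planned. Any titer rise from such an infection inflates the GMR, one-sidedly in the paired analysis.

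The size rests on assumed inputs: factors of about 1.01 to 1.15 for p = 2% to 10% and r = 2 to 4. A reader might infer that noninferiority would be falsely claimed. The documents do not support that, because at the 1.7-fold response from Study 201 the verdict does not change. The bias matters for the GMR as reported, for superiority if the true GMR is near 1, for variant titers, and for noninferiority if the true GMR is near 0.67. It hardly affects SRR. Confidence is high in the omission and its direction, and low in its magnitude.

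**What to change.** In SAP Part B/C Sections 4.4 and 5.5.3.2, exclude from the BD-Day 29 GMT and SRR comparison any participant with a positive RT-PCR after BD-Day 1 through the BD-Day 29 draw, or a positive Elecsys nucleocapsid result at BD-Day 29. Apply the same rule from Day 1 through Day 57 to the PPRSI historical control; in the paired analysis this is largely redundant. Prespecify the comparison with and without the exclusion, and report the two together.

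The cost is SAP wording, since the tests are already planned, and a slightly smaller set. Two limits remain. Very recent infections may still go undetected. The exclusion also conditions on an outcome after the booster: if poor responders are infected more often, removing them raises the booster GMT and again favours noninferiority. Neither version is free of bias, which is why both should be shown.
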